9.4 Responsibilities for Reporting Serious Adverse Events

The Investigator should record all serious adverse experiences that occur during the study period in the appropriate source documents and/or AE log as applicable. The study period for

reporting serious adverse events (e.g. from the time of signing consent to final study visit) should be indicated, who needs to be notified and the time frame for notification. If there are any specific reporting forms to be completed, this should be indicated here. The Investigator will comply with regulations and IRB policy regarding the reporting of adverse events.

10. RISK/BENEFIT ASSESSMENT

10.1 Potential Risks

- Minor trauma to the lips of oropharynx
- Difficulty ventilating through the LMA® Gastro™
- Possibility that device will need to be removed prior to procedure completion, necessitating intubation

10.2 Protection Against Risks

- Appropriate patient selection, avoiding patients with oropharyngeal abnormalities

10.3 Potential Benefits to Subjects

- More secure airway with reduced risk of respiratory compromise and aspiration than treatment with a native airway
- Less likely to have a sore throat than with endotracheal intubation

10.4 Alternatives to Participation

- Management of the airway with an endotracheal tube or with a native airway at the discretion of the anesthesiologist

11. CONFIDENTIALITY OF DATA AND INFORMATION STORAGE

All study participants will be assigned a study number. The PI will maintain the key to the study number and medical record number in a password locked MD Anderson computer. Information about study subjects will be kept confidential and managed according to the requirements of the Health Insurance Portability and Accountability Act of 1996 (HIPAA). Patient data will be entered into a password protected electronic spreadsheet and online database (i.e. REDCap). Only the investigators, who have been invited to participate in the study and who are registered with the IRB, as well as have documented completion of all IRB and HIPAA regulations will have access to patient data, but not the medical record key.

Electronic records will be stored for 5 years after study conclusion on the institution's password protected computer, after which time they will be deleted. If there is a breach in confidentiality or violation of IRB and HIPAA regulations, the IRB will be notified in a timely manner (within 7 days) and appropriate actions taken thereafter. All data used in the analysis and reporting of this investigation will be de-identified. Any photography shall be done in a discrete manner. Should images run the risk of enabling patient identification, identifying characteristics will be obscured electronically prior to publication.

In order to ensure compliance with the Health Insurance Portability and Accountability Act (HIPAA), all subjects enrolled in the study will be required to provide authorization to disclose Protected Health Information (PHI). This authorization will be included in the informed consent document as required by the IRB. In all study reports and in any resulting publications, subjects will not be referred to by their initials and/or study identification number.

12. SAMPLE SIZE DETERMINATION AND DATA ANALYSIS

12.1 Sample Size Determination

- This feasibility study will enroll 30 patients.
- Study success is defined as the ability to place LMA gastro within 3 attempts where completion of the procedure occurs with the LMA® Gastro™ in place.
- The success rate will be estimated using an exact 95% confidence interval.
- Assuming a success rate of 90% (27/30), the limits of an exact 95% confidence interval are (0.73, 0.98).
- The study will be deemed feasible if the study can be completed without crossing any of the stopping boundaries associated with study failure provided by the Bayesian monitoring rule (described below) requiring suspension of patient accrual.

Monitoring of the Failure Rate

- Study failure is defined as inability to place the LMA gastro after 3 attempts or removal of the LMA gastro prior to the completion of the procedure for any reason.
- It will be monitored using the following Bayesian rule: $\Pr(p(F) > 0.10 | \text{data}) > 0.90$, where the probability of failure is denoted by $p(F)$.
- A uniform prior for study failure, $p(F) \sim \text{beta}(1, 1)$, is assumed.
- Therefore, accrual will be suspended if at any time there is a greater than 90% chance that the failure rate exceeds 10%. The Bayesian monitoring of the trial will be in place as mechanism to alert the investigative team of any irregularities or unanticipated occurrences that may arise.

Table 1: Stopping Boundaries for Monitoring **Study Failure**

No. of Patients	Suspend the Trial with this many Study Failures
5	2 to 5
10	2 to 10
15	3 to 15
20	4 to 20
25	5 to 25
30	≥ 5 or max accrual

- using (<http://ibl.mdanderson.org/BTM>) MDA Biostatistics Shiny Applications

Table 2: Operating Characteristics for Monitoring **Study Failure**

True toxicity rate	Probability of Early Termination	Avg. No. of Patients
0.05	0.0968	28
0.1	0.3221	23.6
0.15	0.5725	18.7
0.2	0.7717	14.5
0.25	0.896	11.4

- using (<http://ibl.mdanderson.org/BTM>) MDA Biostatistics Shiny Applications

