Primary Endpoint	Successful completion of ERCP with the LMA® Gastro™ is defined as the ability to place LMA gastro within 3 attempts where completion of the procedure occurs with the LMA® Gastro™ in place.
Feasibility Definition	The study will be deemed feasible if the study can be completed without crossing any of the stopping boundaries associated with study failure provided by the Bayesian monitoring rule requiring suspension of patient accrual.
Brief Analysis Plan	The success rate will be estimated using an exact 95% confidence interval. Assuming a success rate of 90% (27/30), the limits of an exact 95% confidence interval are (0.73, 0.98). Descriptive statistics will be used to summarize all study data. Study failure, defined as inability to place the LMA gastro after 3 attempts or removal of the LMA gastro prior to the completion of the procedure for any reason, will be monitored using the following Bayesian rule: $\text{Pr}(p(F) > 0.10 \text{data}) > 0.90$, where the probability of failure is denoted by $p(F)$. Therefore, we will suspend accrual if at any time there is a greater than 90% chance that the failure rate exceeds 10%.

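### Not crossing a stopping boundary is treated as proof of feasibility, so a trial that crosses none and ends at 26/30 is called feasible while the plan's own posterior gives an 81% chance that failure exceeds 10%

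*Combined protocol and SAP*

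**What the plan says.** The Feasibility Definition row of the Summary Table and section 12.1 give the same criterion. Section 12.1 reads: "The study will be deemed feasible if the study can be completed without crossing any of the stopping boundaries associated with study failure". The Summary Table likewise makes the verdict turn on "if the study can be completed without crossing any of the stopping boundaries" for study failure. Failure means "inability to place the LMA gastro after 3 attempts or removal of the LMA gastro prior to the completion of the procedure for any reason".

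The boundaries come from one rule. In section 12.1, "accrual will be suspended if at any time there is a greater than 90% chance that the failure rate exceeds 10" percent, with a beta(1,1) prior ("A uniform prior for study failure"). Table 1 lists the smallest number of failures that suspends accrual at 5, 10, 15, 20, 25 and 30 patients: 2, 2, 3, 4, 5 and 5. The last row reads "≥ 5 or max accrual". Section 12.1 also describes the monitoring as a way of alerting the team to irregularities.

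No minimum success rate, lower confidence limit or posterior support for an acceptable failure rate is required. Section 12.2 plans descriptive statistics and Clopper-Pearson intervals, and does not connect them to the feasibility verdict.

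**The concern.** The rule is built to detect trouble. It acts only when the data are more than 90% certain that failure exceeds 10%. When it stays silent, all that is known is that this certainty was not reached. The data may support a failure rate below 10%, be indifferent, or favour a rate above 10% by a wide margin. The plan gives all three the same label.

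The title asks whether the device is a feasible alternative for ERCP, and this verdict is the plan's only formal answer. It can therefore be positive while the plan's own model says that failure above 10% is more likely than not. The verdict and the reported interval would then point in different directions within one report.

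**Working it through.** **Inputs, all from section 12.1.** n = 30 ("This feasibility study will enroll 30 patients"); beta(1,1) prior; reference failure rate 0.10; posterior cut-off 0.90; boundaries of Table 1.

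**Step 1: reproduce the plan.** With f failures in n patients, the posterior is Beta(1+f, 1+n−f). The boundary is the smallest f for which Pr(p(F)>0.10|data) is above 0.90. This gives 2, 2, 3, 4, 5, 5, as in Table 1. An exact recursion over the number of failures, with looks at 5 to 25 patients, gives early-termination probabilities of 0.0968, 0.3221, 0.5725, 0.7717 and 0.896 at true failure rates of 5, 10, 15, 20 and 25%, as in Table 2. The exact 95% CI for 27/30 is 0.735 to 0.979, in line with the stated figure. The plan's arithmetic is sound.

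**Step 2: the posterior at n = 30.** For a beta posterior with integer parameters, Pr(p(F)>0.10 | f of 30) = Pr(Bin(31, 0.10) ≤ f). For f = 4 the terms are 0.0382 + 0.1314 + 0.2190 + 0.2352 + 0.1830 = 0.807 (unrounded sum 0.8068).

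| Failures | Successes | Pr(p(F)>0.10 given data) | Verdict if no earlier crossing |
|---|---|---|---|
| 0 | 30/30 | 0.038 | feasible |
| 1 | 29/30 | 0.170 | feasible |
| 2 | 28/30 | 0.389 | feasible |
| 3 | 27/30 | 0.624 | feasible |
| 4 | 26/30 | 0.807 | feasible |
| 5 | 25/30 | 0.917 | boundary crossed |

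At 26/30 the posterior mean failure rate is 5/32 = 15.6%, and the exact 95% CI for success is 0.69 to 0.96.

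**Step 3: can 26/30 be reached without a crossing?** It requires at most 1 failure by patients 5 and 10, 2 by 15, 3 by 20 and 4 by 25. About half of the orderings of 4 failures among 30 patients meet this: at a true rate of 10%, 0.0887 of a binomial probability of 0.1771, which is 0.50. The probability of finishing uncrossed with exactly 4 failures is 0.089 at a true rate of 10% and 0.102 at 15%.

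**Step 4: probability of being deemed feasible.** Add the n = 30 look to the recursion and sum over the uncrossed paths. At a true failure rate of 15%, for 0 to 4 failures: 0.0076 + 0.0404 + 0.0927 + 0.1229 + 0.1016 = 0.365.

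| True failure rate | 1 − Table 2 entry | P(deemed feasible), n = 30 look included |
|---|---|---|
| 5% | 0.903 | 0.900 |
| 10% | 0.678 | 0.647 |
| 15% | 0.428 | 0.365 |
| 20% | 0.228 | 0.164 |
| 25% | 0.104 | 0.059 |

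At a true rate of 15%, the outcomes with 3 or 4 failures, where the posterior favours failure above 10%, make up (0.1229 + 0.1016)/0.3652 = 61% of the feasible verdicts. At 10% they make up (0.1704 + 0.0887)/0.6469 = 40%.

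**Step 5: sensitivity to the schedule of looks.** Table 1 lists looks every 5 patients, but the text says the rule applies at any time. If it is checked after every patient, 26/30 can still finish uncrossed (failures no earlier than patients 5, 11, 18 and 25), with probability 0.049 at a true rate of 10% and 0.056 at 15%. P(deemed feasible) at 15% is then 0.261.

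**The case against.** The strongest reply is that this is a 30-patient, single-arm feasibility study with a prespecified and reproducible rule. How strict a feasibility criterion should be is partly a matter of judgement. The exact CI will be reported whatever the verdict, so a reader of a 26/30 result would see 0.69 to 0.96. One minus the Table 2 entry already approximates the probability of being deemed feasible. All of that is fair, and it limits the weight of the point. It does not remove it, because the verdict takes no account of the interval and Table 2 leaves out the n = 30 look (0.43 against 0.365 at a true failure rate of 15%).

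A reader might infer more than the documents support:

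- *That no criterion on the final data exists.* The n = 30 row of Table 1 does apply the posterior to the complete data. The complaint is that it is lenient and looks in one direction only.
- *That every 26/30 result is called feasible.* About half of the orderings cross an earlier boundary of Table 1 and are not.
- *That 27/30 is the plan's target and could serve as a pass mark.* Section 12.1 writes "Assuming a success rate of 90% (27/30), the limits of an exact 95% confidence interval are (0.73, 0.98") only to show the width of the interval. A 27/30 result would also leave a posterior of 0.62 above 10%.
- *That 10% is a declared maximum acceptable failure rate.* It appears only inside the monitoring rule, together with the 0.90 cut-off.

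**Conclusion.** The point holds as a criticism of the decision criterion. It is not an internal contradiction or an error of arithmetic: Tables 1 and 2 reproduce exactly. Followed as written, the plan can conclude that the device is feasible when its own posterior favours a failure rate above 10%, by 0.62 at 27/30 and 0.81 at 26/30, provided that no earlier boundary was crossed. A device with a true failure rate of 15% would be deemed feasible with probability 0.365, and one with 20% with probability 0.164.

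These figures assume the beta(1,1) prior, independent patients with a constant failure rate, and looks as in Table 1. Checking after every patient lowers the probabilities but leaves the conclusion unchanged.

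**What to change.** 1. Keep Table 1 unchanged, as the rule for suspending accrual only.
2. In section 12.1 and in the Feasibility Definition row of the Summary Table, word a completed, uncrossed trial as not shown to exceed a 10% failure rate. Base the conclusion on the final Pr(p(F)>0.10|data), reported beside the exact 95% CI.
3. Add to Table 2 a column for the probability of being deemed feasible that includes the n = 30 look: 0.900, 0.647, 0.365, 0.164 and 0.059.

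Do not add a 27/30 pass mark, for the reasons given above.

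The cost is a change of wording in two places, one column and one posterior figure in the report. No extra patients or data are needed, and the suspension of accrual does not change. The downside for the sponsor is a conclusion worded less favourably than a plain statement of feasibility.

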The LMA® Gastro™ represents a novel device with the ability to facilitate direct endoscopic access via the integrated endoscopic channel. Although the utility for esophagogastroduodenoscopy has been demonstrated(11), a similar feasibility study has not been conducted for ERCP procedures. The utility of the LMA® Gastro™ may be less for ERCPs, as ERCP procedures require multiple small movements to enable cannulation of the bile duct and frequent advancement or retraction of the endoscope in order to successfully complete the procedure. It is possible that the presence of the LMA tube will make these maneuvers more challenging. The goal of this study is to determine the feasibility of the LMA® Gastro™ for ERCP.

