A standard sideviewing duodenoscope measuring 11.3mm in maximum diameter will be lubricated with KY jelly by the gastroenterologist, coating the full length of the endoscope that will be inserted into the LMA® Gastro™.

Should the LMA® Gastro™ impede completion of the procedure, the anesthesiologist will remove the LMA® Gastro™ and either proceed with a native airway or place an endotracheal tube. This decision will be at the discretion of the anesthesiologist.

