7.4 Additional Data Collected by Research Coordinator

- Number of attempts required to place the LMA® Gastro™ (See Appendix 2)
- Removal of the LMA® Gastro™ prior to completion of the procedure (See Appendix 2)
- Any adverse events (See Appendix 2)
- Gastroenterologist device satisfaction survey (See Appendix 3)
- Anesthesiologist device satisfaction survey (See Appendix 3)

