12.2 Planned Statistical Analysis

Descriptive statistics will be used to summarize all study data. Frequencies and percentages will be used to summarize the failure and success rates. Interval estimation of rates will be provided using Clopper-Pearson exact 95% CIs. Visualization techniques (such as bar graphs, line graphs, etc.) will be used to illustrate distribution of the number of LMA® Gastro™ attempts and other select study outcomes. Surveys for gastroenterologist and anesthesiologist satisfaction with the LMA® Gastro™ contain items measured on a 10-point Likert scale with 1 reflecting strong disagreement and 10 strong agreement. Mean scores and standard deviations will be used to provide summaries for each survey item. Summaries will be stratified by gastroenterologist and anesthesiologist. Paired differences in survey items between gastroenterologist and anesthesiologist scores will be summarized using descriptive statistics and 95% CIs. Finally, some patients will have the same anesthesiologist or gastroenterologist who performs the ERCP; therefore, descriptive summaries of study outcomes will be conducted by anesthesiologist and gastroenterologist to explore for the potential of a clustering effect.

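### Does the monitored failure definition leave out patients who are not successes?

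*Combined protocol and SAP*

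**What the plan says.** The Summary Table and Section 12.1 carry the same pair of definitions. Success is the "ability to place LMA gastro within 3 attempts where completion of the procedure occurs with the LMA® Gastro™ in place". For failure, Section 12.1 has "Study failure is defined as inability to place the LMA gastro after 3 attempts or removal of the LMA gastro prior to the completion" (that is, of the ERCP). The Brief Analysis Plan row of the Summary Table says the same, and both places extend this to removal from any cause.

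The two counts have different uses. The exact 95% confidence interval is for the success rate. The Bayesian rule, with a uniform prior, suspends accrual when the posterior probability that the failure rate exceeds 10% is above 0.90. The verdict follows the failure count: "The study will be deemed feasible if the study can be completed without crossing any of the stopping boundaries associated with study failure".

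Other sections bear on the reading:

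- Section 12.2: "Frequencies and percentages will be used to summarize the failure and success rates".
- Section 7.2: "Should the LMA® Gastro™ impede completion of the procedure, the anesthesiologist will remove the LMA® Gastro™", with a native airway or an endotracheal tube to follow.
- Section 7.4 lists the number of attempts and early removal as separate data items, both recorded on Appendix 2.
- Section 7.5 counts each passage of the device into the oropharynx as an attempt.
- Section 8 allows withdrawal by clinician decision, without saying how such a patient is counted.

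**The concern.** Read word for word, the two definitions may not cover everyone. Two kinds of patient look stranded:

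1. **Placement abandoned after one or two attempts.** The device was not placed, so this is no success. Three attempts were not made, so the first limb of failure is not met.
2. **ERCP not accomplished while the device stays in.** Section 2 itself warns of difficulty: "It is possible that the presence of the LMA tube will make these maneuvers more challenging". Section 7.2 deals only with the case where the device is then taken out.

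If such patients are neither successes nor failures, the two reported rates need not sum to 100%. The trial could then be declared feasible on a failure count that omits them, while the primary estimate treats them as non-successes. The boundaries are low (2 failures at 10 patients, 5 at 25), so a single classification can decide whether accrual is suspended.

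**Working it through.** **Inputs (Section 12.1).** Prior beta(1, 1); rule Pr(p(F) > 0.10 | data) > 0.90; looks at 5, 10, 15, 20, 25 and 30 patients; 30 patients in all.

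**The plan's own figures.** With x failures in n patients the posterior is beta(1 + x, 1 + n − x), and the boundary is the smallest x whose tail above 0.10 exceeds 0.90.

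- Boundaries: 2, 2, 3, 4, 5, 5, as in Table 1.
- Clopper-Pearson 95% limits for 27/30: 0.7347 and 0.9789, which round to the stated 0.73 and 0.98.
- Early termination by exact binomial recursion, looks at 5 to 25 only: 0.0968, 0.3221, 0.5725, 0.7717, 0.8960 at true rates 0.05 to 0.25, as in Table 2. Table 2 therefore does not count a crossing at 30 as early termination.

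These figures depend only on p(F), so no reading of the definitions alters them.

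**Patient type 2, one meaning of completion used in both definitions.**

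| Meaning of completion | ERCP not accomplished, device still in |
|---|---|
| End of the procedure | Completion occurred with the device in place: success |
| Technical accomplishment | Completion never occurred; the device later came out before it: failure |

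Either way the patient is classified. A gap appears only if removal is narrowed to removal during the procedure.

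**Patient type 1.** The phrases within 3 attempts and after 3 attempts are written as opposites. A device passed into the oropharynx and finally taken out, with no ERCP done through it, fits removal before completion from any cause. Not every withdrawal between attempts can count, since a patient placed on the second attempt would then be both success and failure. Counting only the final withdrawal avoids this. The text does not spell that step out, but it is the natural one.

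**Signs that a complement was meant.** An assumed 90% success rate is paired with a 10% failure threshold (100% − 90% = 10%). The Summary Table lists the rate of successful placement as a secondary objective, and Section 1 lists the rate of unsuccessful placement for the same objective. Section 12.2 reports both rates together.

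**What one patient can do.** At the 25-patient look with 4 counted failures and 1 type 1 patient:

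| Handling | x / n | Pr(p(F) > 0.10) |
|---|---|---|
| Kept as a non-failure | 4/25 | 0.888, continue |
| Left out | 4/24 (not a Table 1 row) | 0.902 |
| Counted as a failure | 5/25 | 0.960, suspend |

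**Overall effect, on assumed rates only.** Take 7% failures on the literal wording and add type 1 patients as failures. The probability of crossing before 30 is:

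| Assumed rate of type 1 patients | Total failure rate | Crossing before 30 |
|---|---|---|
| 0% | 7% | 0.177 |
| 1% | 8% | 0.223 |
| 2% | 9% | 0.272 |
| 5% | 12% | 0.425 |

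Neither the 7% nor the added rates come from the documents.

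**The case for a change.** The strongest case for a change is that intent is not text. Section 7.2 speaks of removal when the device gets in the way of the procedure, and Section 7.4 records attempts and removal separately, so taking out a device that was never seated may not be what removal means. In a single-arm study, classifying a borderline patient after seeing the running count leaves room for discretion.

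The sharpest illustration has 25 successes, 4 counted failures and 1 unclassified patient among 30, with no earlier crossing. Success is 25/30 = 83.3% (exact 95% CI 0.653 to 0.944). The posterior is 0.807 with 4 failures and 0.917 with 5, so the verdict appears to flip. One added sentence would prevent it.

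Part of this stands: an abandoned placement is not expressly classified, and a clarifying sentence would do no harm. The illustration is weaker than it looks. At 30 patients no accrual remains to suspend, the last row of Table 1 also names maximum accrual, and Table 2 leaves that look out of early termination. Whether 5 failures at 30 would overturn feasibility is thus a separate question of reading. The configuration is also selected: at an assumed 7% failure rate, exactly 4 failures at 30 with no earlier crossing has probability about 0.05, before an unclassified patient is required as well. The 25-patient look makes the point without this difficulty.

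A fuller repair would also have to settle denominators, withdrawals and whether ERCPs that fail for reasons unrelated to the device count against it. Those are design choices beyond a wording slip.

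**Conclusion.** No change to the plan is called for. This is a gap in wording that analysts would fill sensibly, by counting an abandoned placement as a failure. An ERCP not accomplished with the device in place is at most ambiguous, and falls into one class or the other once completion is given a single meaning. No stated number or boundary is wrong.

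The possible effect is one patient's classification near a boundary (0.888 against 0.960 at the 25-patient look). Its overall size cannot be stated without assumed rates, and it is nil if no such patient occurs. The conclusion rests on reading success and failure as complements, which the plan's wording and its 90%/10% pairing support. Appendix 2, where attempts and removals are recorded, is not in the text available for review and may already settle the classification.

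### The monitoring rule is written as continuous, but Table 2 holds only for looks after 5, 10, 15, 20 and 25 patients, and the feasibility verdict depends on which schedule applies

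*Combined protocol and SAP*

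**What the plan says.** - **Rule.** Section 12.1 (Monitoring of the Failure Rate): "accrual will be suspended if at any time there is a greater than 90% chance that the failure rate exceeds 10" percent. The Brief Analysis Plan in the Summary Table: "we will suspend accrual if at any time there is a greater than 90% chance that the failure rate exceeds 10" percent. Neither sentence names a cohort size or a minimum number of patients before the first check.
- **Prior.** "A uniform prior for study failure", given as beta(1, 1), in section 12.1.
- **Table 1.** Limits are listed at 5, 10, 15, 20, 25 and 30 patients: 2, 2, 3, 4, 5 and 5 failures. The last row reads "≥ 5 or max accrual".
- **Table 2.** The column "Probability of Early Termination" shows 0.0968, 0.3221, 0.5725, 0.7717 and 0.896 at true rates 0.05, 0.10, 0.15, 0.20 and 0.25. The average numbers of patients are 28, 23.6, 18.7, 14.5 and 11.4. No look schedule is stated.
- **Feasibility.** "The study will be deemed feasible if the study can be completed without crossing any of the stopping boundaries", meaning the boundaries that the Bayesian monitoring rule supplies. This appears in the Summary Table and in section 12.1.

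**The concern.** A rule that acts at any time is checked after each patient. Table 1 lists only six sample sizes, and Table 2 does not say when the checks take place. If Table 2 was computed for checks every five patients, it understates how often the written rule stops the trial and overstates the average number of patients treated.

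More than the operating characteristics is at stake. Crossing a boundary is the only criterion by which the study is called feasible or not, so the look schedule is part of that criterion. If it is left open, the same 30 outcomes can be reported as feasible or not feasible, and the choice could be made after the data are seen.

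**Working it through.** **Inputs**, all from section 12.1: prior beta(1, 1); suspend if Pr(p(F) > 0.10 | data) > 0.90; maximum 30 patients; Tables 1 and 2.

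**Step 1: posterior.** With x failures in n patients the posterior is Beta(1 + x, 1 + n − x). Its probability above 0.10 equals the binomial probability P(Bin(n + 1, 0.10) ≤ x). For example, 1 failure in 3 gives P(Bin(4, 0.10) ≤ 1) = 0.6561 + 0.2916 = 0.948, which is above 0.90. One failure in 5 gives 0.531 + 0.354 = 0.886, which is not.

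**Step 2: smallest crossing count at each n.**

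| Patients | Failures needed |
|---|---|
| 1–4 | 1 |
| 5–10 | 2 |
| 11–17 | 3 |
| 18–24 | 4 |
| 25–30 | 5 |

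All six Table 1 limits (2, 2, 3, 4, 5, 5) are reproduced, so Table 1 is correct at the sizes it lists.

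**Step 3: where the text and Table 1 part.** The written rule can be crossed without the next Table 1 row being crossed in three ranges:
- n = 1–4: one failure gives 0.990, 0.972, 0.948 and 0.919, but the row for 5 patients needs 2.
- n = 16–17: three failures give 0.917 and 0.902, but the row for 20 needs 4.
- n = 21–24: four failures still give 0.902 at n = 24, but the row for 25 needs 5.

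**Step 4: Table 2.** I used an exact binomial recursion over patients, absorbing at each look where the limit is met. Entries are the probability of stopping before patient 30, with average N in brackets.

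| True failure rate | Table 2 as printed | Looks at 5, 10, 15, 20, 25 | Every patient from 5 | Every patient from 1 |
|---|---|---|---|---|
| 0.05 | 0.0968 (28) | 0.0968 (28.0) | 0.1098 (27.8) | 0.2281 (24.1) |
| 0.10 | 0.3221 (23.6) | 0.3221 (23.6) | 0.3787 (22.7) | 0.4969 (18.0) |
| 0.15 | 0.5725 (18.7) | 0.5725 (18.7) | 0.6570 (17.2) | 0.7316 (12.7) |
| 0.20 | 0.7717 (14.5) | 0.7717 (14.5) | 0.8469 (12.9) | 0.8824 (8.8) |
| 0.25 | 0.896 (11.4) | 0.8960 (11.4) | 0.9438 (9.9) | 0.9573 (6.3) |

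Of the schedules tried, only looks at 5, 10, 15, 20 and 25 match all ten printed values. Patients 1–4 account for part of the gap between the printed table and checks from patient 1. At 0.05 the share is (0.2281 − 0.1098)/(0.2281 − 0.0968) = 90%. At the other rates it is 68%, 47%, 32% and 22%.

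**Step 5: crossing any boundary up to and including n = 30.** If the row for 30 patients counts, this is the probability of a not-feasible verdict. The last two columns give the probability that the every-patient rule is crossed while no Table 1 row is.

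| True failure rate | Table 1 looks | Every patient from 5 | Every patient from 1 | Opposite verdict, from 5 | Opposite verdict, from 1 |
|---|---|---|---|---|---|
| 0.05 | 0.1003 | 0.1104 | 0.2286 | 0.010 | 0.128 |
| 0.10 | 0.3531 | 0.3842 | 0.5010 | 0.031 | 0.148 |
| 0.15 | 0.6348 | 0.6671 | 0.7391 | 0.032 | 0.104 |
| 0.20 | 0.8362 | 0.8562 | 0.8893 | 0.020 | 0.053 |
| 0.25 | 0.9406 | 0.9495 | 0.9615 | 0.009 | 0.021 |

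**Step 6: single sequences.**
- One failure in patient 3 and 27 successes after it: the posterior is 0.948 at n = 3, so the written rule suspends. No Table 1 row is crossed.
- Failures only in patients 8, 13 and 17, which is 27/30, the protocol's planning scenario: the posterior at n = 17 is 0.902, so the written rule suspends. At the Table 1 sizes the counts are 0, 1, 2, 3, 3, 3 against limits 2, 2, 3, 4, 5, 5, so none is crossed.
- Over all C(30, 3) = 4060 orderings of three failures, a boundary is crossed in 1130 (27.8%) under Table 1, 1265 (31.2%) with every-patient checks from patient 5, and 1941 (47.8%) from patient 1.

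**The case against.** The strongest reply is that Table 1 is itself the schedule. The feasibility definition points to boundaries described below it, the only ones listed are in Table 1, and Table 2 follows from the same sizes. On that reading nothing printed is miscalculated, and the phrase at any time is merely loose. The reading is plausible, but no sentence confines the checks to those sizes. The operative sentence, printed twice, says otherwise, and Table 1 can equally be read as sample values of a continuous rule.

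Second, the largest differences come from letting one failure among the first four patients stop the trial, which may not be intended. That is fair. From patient 5 the opposite-verdict probability is at most 0.032, and the 8/13/17 example clears the threshold by only 0.002. The conflict is smaller on that reading but remains: at a true rate of 0.15, early termination is 0.657 against the printed 0.573.

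Third, Table 2 is labelled as early termination, so leaving out n = 30 suits its label. I agree, and do not call that an error. Whether the row for 30 patients counts toward feasibility is also open, because accrual is complete by then. It does stand in the table of stopping boundaries, so the protocol should settle the point.

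Fourth, section 12.1 describes the monitoring as a way to alert the team. That limits the consequence of a suspension. It does not limit the consequence for feasibility, which the definition ties to a crossing.

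**Conclusion.** The concern holds. The written rule does not have the operating characteristics printed in Table 2. At a true failure rate of 0.05 the printed probability of early termination is 0.097; the written rule gives 0.110 if checked from patient 5 and 0.228 from patient 1. At 0.10 the figures are 0.322, 0.379 and 0.497. The chance that the text and Table 1 disagree on feasibility is 0.9% to 3.2% with checks from patient 5 and 2.1% to 14.8% from patient 1, across the five tabulated rates.

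Three assumptions apply. The Table 2 schedule is inferred from exact agreement on every row, because the protocol does not state it. Outcomes are treated as independent with a constant failure rate. The opposite-verdict figures compare full 30-patient sequences and count the n = 30 row. The individual Table 1 limits and the exact interval (0.73, 0.98) for 27/30 are correct and unaffected. This needs to be fixed because it bears on the study's only decision criterion.

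**What to change.** Reconcile the rule in the Summary Table and section 12.1 with Tables 1 and 2, in one of two ways.

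- **(a) Scheduled looks.** Replace the at-any-time wording in both places with a statement that the rule is applied at the Table 1 reviews (after 5, 10, 15, 20, 25 and 30 patients). Label Table 2 as the probability of stopping before patient 30. If the n = 30 row counts, add a column for crossing any boundary including it: 0.100, 0.353, 0.635, 0.836, 0.941. Cost: one phrase in two places and one column.
- **(b) Continuous monitoring.** List the boundary for every n, state the first patient at which the rule applies, and replace Table 2 with the matching values from Step 4, adding the Step 5 probabilities through n = 30. Cost: two recomputed tables and one sentence.

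Under either option, state in the feasibility definition which boundaries count, including whether the row for 30 patients does. Neither option needs extra patients.
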